#### I. Purpose, Background and Rationale

#### A. Aims and Hypotheses

Nearly 12 of the 34 million adult smokers in the US smoke menthol cigarettes. When added to cigarettes, menthol increases addictive potential and dependence, and decreases the likelihood of cessation. These effects are particularly felt in the African American (AA) community where targeted marketing has resulted in  $\approx$ 85% of AA versus  $\approx$ 20% of White smokers using menthol cigarettes. The FDA's decision to advance the rulemaking process to ban menthol cigarettes is an important step toward closing the gap in tobaccorelated disease and death disproportionately experienced by AA smokers. The agency's regulatory action stopped short of including menthol-flavored e-cigarettes (ECs) and debate continues about whether more comprehensive enforcement priorities inclusive of menthol flavored e-liquids should be enacted. While a ban on menthol flavored EC liquids may reduce youth and young adult initiation, it may also discourage adult menthol smokers to switch from tobacco cigarettes to EC. This could slow harm reduction and result in a negative public health impact that would be concentrated in racial/ethnic minority communities already disproportionately burdened by tobacco. FDA has identified the impact of EC flavoring on smoking patterns as a research priority area, and there is an **urgent need** for studies that examine tobacco regulatory actions with a specific focus on possible unintended consequences that may increase tobaccorelated health disparities. To date, a prospectively designed randomized clinical trial (RCT) has not been conducted; therefore, the efficacy of menthol-flavored versus tobacco-flavored EC to facilitate switching from combustible cigarettes to EC in adult menthol smokers is not known. Our experienced, multidisciplinary team is one of the only groups in the country exclusively focused on tobacco-related health disparities intervention research in the AA community. Our recently completed RCT provided menthol EC or tobacco EC to AA and Latinx adult smokers. Among menthol smokers, post-hoc analyses found equivalent rates of switching from tobacco cigarettes to EC, tobacco harm reduction, EC product use, and acceptability between those who used tobacco EC versus menthol EC, although the study was not prospectively designed for this purpose and is limited by a small sample size for these comparisons. These data are consistent with observational studies that have found that nicotine - not flavor - drive use in adult EC users and provide strong preliminary evidence to support restrictions on menthol flavored EC given potential benefit to youth and lack of evidence of harm to smokers. However, to empirically answer this question, a fully powered RCT is needed.

The objective of this application is to provide much needed data to the FDA to guide regulatory action on EC flavoring. Menthol smokers (n=800), stratified by race and gender, will be randomized 1:1 into a 12-week open label, non-inferiority trial comparing a 4th generation nicotine salt-based pod-system EC in menthol- versus tobacco-flavored e-liquid. Follow-up will continue through week 26. The central hypothesis is that tobacco EC are not inferior to menthol EC at facilitating a switch to EC in menthol cigarette smokers.

Our specific aims are:

- 1) Compare the effectiveness of menthol versus tobacco EC at facilitating switching at week
  - **12.** Hypothesis 1: Participants randomized to tobacco EC (versus menthol EC) will demonstrate non-inferior rates of complete and predominant switching to EC (primary outcome). Complete switching is defined as exclusive use of EC, confirmed with CO < 6 ppm, and predominant switching is defined as use of EC with > 50% reduction in CPD. Rates of complete and predominant switching will also be compared separately by group.

- 2) Compare tobacco harm reduction of menthol versus tobacco EC at week 12. Participants randomized to tobacco EC (versus menthol EC) will demonstrate comparable (i.e., no statistically significant differences) change in CO, respiratory symptoms, lung function, blood pressure, and tobacco-related quality of life from baseline to week 12.
- 3) Compare the acceptability of menthol versus tobacco EC at week 12. Hypothesis 3: Participants randomized to tobacco EC (versus menthol EC) will consume comparable amounts of study provided e-liquid (measured in grams) and demonstrate comparable reductions in cigaretterelated withdrawal, craving, and dependence. Subjective effects of vaping will also be compared between groups.
- **4) Examine the long-term effectiveness of menthol versus tobacco EC at week 26.** Switching patterns at week 26 will be compared to examine long-term maintenance of EC and smoking patterns under naturalistic conditions (EC only provided up to week 12). Hypothesis 4: There will be no statistically significant difference in rates of complete or predominant switching at week 26 between those randomized to menthol versus tobacco EC.

#### **B. Background and Significance**

**Electronic cigarettes as a harm reduction strategy for adult cigarette smokers**. Tobacco, but primarily cigarettes, remains the leading cause of preventable disease in the US, claiming 480,000 lives per year and affecting an additional 16 million smokers who suffer from smoking-related chronic diseases. Eliminating tobacco use in adult cigarette smokers remains the primary end-game for reducing tobacco's public health burden, but tobacco harm reduction has emerged as an important complement to these efforts. Specifically, the availability of potentially less harmful products has led to increased focus on replacing all forms of combustible tobacco with noncombustible nicotine products that deliver nicotine but fewer tobacco toxicants to adults who cannot or are not ready to quit cigarettes. Central to harm reduction is the fact that nicotine contributes relatively little harm compared to the deleterious effects of combustible tobacco.

Electronic cigarettes (ECs) have emerged as an effective harm reduction strategy for individuals who smoke cigarettes who cannot or will not quit using FDA-approved cessation methods. EC are used by one in six US adult cigarette smokers and are now the most common assisted method of quitting cigarettes. Exclusively switching from cigarettes to ECs optimizes harm reduction relative to continued smoking and growing evidence indicates that partially switching to EC reduces cigarette consumption, is a marker of EC acceptability, and might also be associated with reduced harm, particularly for cancer and COPD. In our RCT that directly informs the current study, partial switchers replaced > 75% of their cigarettes with EC, resulting in a decrease of 70 cigarettes per week from baseline and significant reductions in the potent lung carcinogen, NNAL, carbon monoxide, and respiratory symptoms. Current estimates indicate that 6.6 million premature deaths could be prevented over the next decade in the US and 86.7 million fewer years of life lost if adult cigarette smokers switched to EC.

**Menthol flavoring in cigarettes.** Menthol is a flavor additive with a minty taste and aroma that, when added to cigarettes, increases appeal and addictive potential, reduces the irritation and harshness of smoking, leads to greater depth of inhalation of tobacco smoke and its harmful constituents, facilitates dependence, and decreases the likelihood of cessation. Targeted tobacco industry marketing of menthol cigarettes to African American (AA) communities since the 1940s has led to disproportionately higher rates of menthol cigarette use. Today, 85% of all AA smokers smoke menthol cigarettes compared to 20% of Whites. Despite similar smoking prevalence, smoking on fewer days, and lower overall levels of daily cigarette consumption, AAs are two to three-times more likely to die of tobacco-related illnesses, including cancer and heart disease, than other racial/ethnic groups;  menthol cigarettes are believed to be a major reason for this disproportionate suffering among AA smokers. Simulation modeling estimated that if the US had implemented a menthol cigarette ban in 2011, 190,000 Black lives and 633,000 deaths, overall, would have been averted by 2050. *The FDA's monumental decision to advance the rulemaking process to ban menthol cigarettes is an important step toward closing the gap in tobacco-related disease and death disproportionately experienced by AA smokers.* 

**Menthol flavoring in EC.** The FDA's regulatory action on April 29, 2021 stopped short of including menthol-flavored ECs and debate continues about whether more comprehensive enforcement priorities inclusive of menthol flavored e-liquids should be enacted. At present, FDA is calling for research that examines the impact of EC flavoring on tobacco use behaviors with a particular focus on possible unintended consequences of tobacco regulatory actions on populations disproportionately burdened with tobacco-related health disparities. *The current proposal directly responds to this call and, to our knowledge, will be the first prospectively designed study to directly compare the efficacy of menthol* 

versus tobacco EC at facilitating switching from tobacco cigarettes to EC in adult menthol smokers transitioning to EC. We anticipate enrolling > 80% racial/ethnic minorities (primarily AA and Latinx) into the current study, thereby focusing on the populations who will be most impacted by regulatory action on menthol.

#### C. Rationale

Innovation in this application lies in the methods applied to the research question and the population studied. The status quo as it pertains to understanding the role of EC flavoring in adult smoker's tobacco use behaviors is to conduct observational and lab-based studies. (35, 37, 38, 40, 41, 45, 46) (42) These designs contribute important information about the association between EC flavors and switching, but they cannot determine causality and are limited by self-selection bias. To definitively answer the question about the efficacy and acceptability of menthol EC versus tobacco EC at facilitating switching in adult smokers, an RCT is needed to establish if the observed associations are due to self-selection or are truly causal. In that regard, the research proposed in this application is innovative, because it represents a departure from the status quo by being the first RCT to directly compare EC flavoring in adult menthol smokers interested in switching. Results from our preliminary studies (see C3) suggest comparable rates of switching from tobacco cigarettes to EC, tobacco harm reduction, EC product use, and acceptability between adult menthol smokers who used tobacco EC versus menthol EC and, in doing so, provide compelling evidence for conducting a fully powered RCT comparing menthol and tobacco EC. In addition, racial/ethnic minorities in the US are more likely to smoke menthol cigarettes and will be most impacted by regulatory action on menthol as a characterizing EC flavor, yet these groups are underrepresented in existing observational and lab-based studies examining the role of EC flavoring on adult smoker's tobacco use behaviors. The research proposed in this application is further innovative, as it represents a departure from the status quo in that we will conduct the largest intervention trial of racial/ethnic minority menthol smokers ever done. We anticipate > 80% representation from racial/ethnic minority groups, primarily AA and Latinx. Results have the potential to shift paradigms. Specifically, based on our strong preliminary data, we expect that both menthol and tobacco EC will be acceptable and result in high rates of switching and improvements in tobacco-related health effects. The study will provide critical data to the FDA to inform regulatory action of menthol EC that could slow youth and young adult initiation with no resulting negative impact on switching in adult combustible cigarette smokers transitioning to EC and no unintended consequences in a priority population of predominately AA and Latinx smokers.

## II. Research Plan and Design

#### A. Study Objectives

This study will examine the short- and long-term effectiveness, tobacco harm reduction, and acceptability of menthol versus tobacco EC in adult menthol smokers not interested in quitting nicotine but interested in switching from cigarettes to EC.

#### B. Study Type and Design

Menthol smokers (n=800), stratified by race and gender, who are not interested in quitting nicotine will be randomized 1:1 into a 12-week open label, non-inferiority trial comparing a 4th generation nicotine salt-based pod-system EC in menthol or tobacco flavoring. Each group will be provided a 12-week supply of EC 5% nicotine concentration in either menthol or Virginia tobacco and will complete 4 check-in sessions to facilitate switching to EC. The primary outcome is the proportion who make a complete or predominant switch to EC at week 12, where complete switching is defined as exclusive use of EC, biochemically confirmed with CO < 6, and predominant switching is defined as use of EC with > 50% reduction in CPD. Secondary outcomes include acceptability and long-term effectiveness. Follow-up will continue through week 26 to examine long-term maintenance of EC product use and smoking behavior under naturalistic conditions. Participants will be recruited and enrolled in collaboration with The University of Kansas Health System and Swope Health Central (Swope), a federally qualified health center serving a predominately AA population, that has been the site for our previous trials.

**Why a non-inferiority trial?** Non-inferiority trials are executed when one product is anticipated to be 'not unacceptably worse than' a comparator product and have value when it is feasible to sacrifice some degree of benefit to gain advantages provided by another product.  In the case of EC flavoring, the tradeoff of lower efficacy and acceptability of tobacco EC to adult menthol smokers may be well worth the advantages gained in youth and young adult initiation so long as the difference between tobacco and

menthol EC is not so large that adult menthol smokers are unwilling to use tobacco EC. The alternative would be a superiority study, but these are used to conclude that one product is better than the other, and at the time of this proposal there is no data supporting this approach that menthol EC are more effective than tobacco EC at facilitating a switch from tobacco cigarettes to EC or vice versa. Rather, data from our RCT and other studies suggest that tobacco EC are non-inferior to menthol EC in terms of effectiveness and acceptability to adult users, but a fully powered RCT is needed.

#### C. Sample size, statistical methods, and power calculation

Sample size calculation. The aim of this non-inferiority trial is to establish that tobacco EC are not inferior to menthol EC in terms of the primary outcome, which is the proportion of menthol smokers who make a complete or predominant switch to EC, defined as use of EC along with a > 50% reduction in cigarettes from baseline to week 12. We assume 1) based on our RCT, that 73% in the menthol EC group will be complete or predominant switchers at week 12. We arrived at the 73% estimate at week 12 by examining the trend in switching from week 2 to week 6 in our RCT. Specifically, we noted a 12% reduction in switching from week 2 to week 6 and assumed that a similar trend would continue through week 12. Given an 85% switch rate in the menthol EC group at week 6 in our RCT and assuming a 12% reduction in switching from week 6 to 12, gives us a 73% switch rate at week 12. We also assume 2) to prove non-inferiority, the proportion in the tobacco EC group that are complete and partial switchers at week 12 will be similar to the menthol EC as long as it is greater than 64%. So, we can assume that P1=the proportion in the tobacco EC group that will be complete or predominant switchers at week 12=0.64 and that P2= the proportion in the menthol EC group that will be complete or predominant switchers at week 12=0.73. Then to test for noninferiority we have the following hypotheses: H0 (null hypothesis): P1-P2  $\leq$  -0.09 and H1 (alternative hypothesis): P1-P2 > -0.09. Following these assumptions 400 per group gives us 82% power with a Type 1 error rate of 2.5% using a normal approximation test for non-inferiority. Sample size calculations were done with PASS 16.0.4. **Basis for sample size calculations.** Estimates for non-inferiority trials are guided by an effectiveness ratio that indicates how effective one product is relative to another product and is determined from estimates on the outcome of interest and the a priori difference threshold. The FDA and other regulatory bodies have established an effectiveness ratio of  $\geq$  80% to indicate bioequivalence (i.e., non-inferiority). This is the criterion that we used in determining sample size for this study. Recent tobacco non-inferiority studies, including a tobacco harm reduction study comparing EC to heat-not-burn, have used a difference threshold of 15%.  Using this 15% threshold and our estimate of a 73% complete or predominant switch rate in the menthol EC group gives us an effectiveness ratio of 79% (.58/.73), which is under the criteria set by FDA. Raising the difference threshold to 14% would give us an effectiveness ratio of 81% (.59/.73). While this meets FDA criteria for non-inferiority, we felt that a difference of 14% was too large. Rather, we have gone with a more stringent difference threshold of 9%; at this threshold the proposed effectiveness ratio for our study is 88% (.64/.73), meaning that tobacco EC will be assumed to not be inferior to menthol EC if they are at least 88% as effective at facilitating a complete or predominant switch as menthol EC. This criterion places us well above the equivalence threshold set by the FDA and is more conservative than similar tobacco harm reduction non-inferiority studies, which we believe is a strength of this study. Missing **data.** We expect minimal (<5%) lost to follow-up at week 12 based on our recent studies, however those lost will be considered as non-complete or predominant switcher and will be imputed as such.

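### The 73% week-12 menthol rate carries a 4-week decline over 6 weeks without adjusting for the longer interval; at the observed pace power is about 77% to 79%, not 82%

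*Combined protocol and SAP*

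**What the plan says.** All of the relevant text is in section II.C (Sample size, statistical methods, and power calculation), apart from the design statement in II.B and the decision rule under Aim 1.

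- **Basis of the control rate.** From the sponsor's earlier trial: "we noted a 12% reduction in switching from week 2 to week 6 and assumed that a similar trend would continue through week 12".
- **How it is applied.** Starting from 85% in the menthol group at week 6: "assuming a 12% reduction in switching from week 6 to 12, gives us a 73% switch rate at week 12".
- **Margin.** An absolute difference: "we have gone with a more stringent difference threshold of 9" percentage points. The plan expresses this as a limit of 0.64 and a ratio of 88% (0.64/0.73).
- **Power.** "400 per group gives us 82% power with a Type 1 error rate of 2.5% using a normal approximation test for non-inferiority".
- **Missing data.** Loss at week 12 is expected to be below 5%, and "those lost will be considered as non-complete or predominant switcher and will be imputed as such". The derivation of the 73% and of the 400 per group mentions no allowance for this.

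**The concern.** The stated reason for 73% is that an observed trend continues, and a trend has a time unit. The decline was seen over 4 weeks, but the same amount is spread over the following 6, an interval half as long again. The figure therefore does not follow from the reason given for it.

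Power is at stake. With a fixed margin on the difference scale, the variance of the estimated difference grows as the common rate moves towards 50%. A control rate below 73% therefore means less power for the same 400 per arm. The plan presents the study as the fully powered trial that the question needs, and under Aim 1 a lower confidence limit at or below −0.09 can leave the result inconclusive. How often that would happen with equally effective products is something the reader should be able to rely on.

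The loss-to-follow-up rule acts in the same direction. Counting lost participants as non-switchers lowers the analysed rate in both arms.

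**Working it through.** **Inputs (II.B and II.C).** 400 per arm, 1:1; margin 0.09; one-sided type 1 error 2.5% (critical value 1.96); menthol rate 85% at week 6; decline of 12% over weeks 2 to 6; loss below 5%, counted as non-switching.

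**Formula.** Normal approximation with unpooled variance and the same true rate p in both arms:

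Power = Φ(0.09 / √(2p(1 − p)/400) − 1.96)

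**Reproducing the plan's figure.** At p = 0.73 the standard error is √(2 × 0.73 × 0.27/400) = 0.0314. Then 0.09/0.0314 − 1.96 = 0.907 and Φ(0.907) = 81.8%, which agrees with the stated 82%. Simulating the 95% confidence interval rule gives 81.9%. The 82% therefore rests on equal true rates of 73%. The plan writes P1 = 0.64, but that is the margin boundary; taken as the true tobacco rate it would give only 2.5%.

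**Extrapolating over the right interval.**

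- In points: 12/4 = 3 points per week; 3 × 6 = 18; 85 − 18 = 67%. On this line 73% is the week-10 value (85 − 3 × 4).
- As a relative decline at constant pace: 0.85 × 0.88^(6/4) = 0.85 × 0.8255 = 70.2%.
- As the plan did it: 85 − 12 = 73%, or 12/6 = 2 points per week.

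The subtraction 85 − 12 indicates that the plan treats the 12% as points. A single relative reduction would have given 0.85 × 0.88 = 74.8%.

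**Power with 400 per arm.** The last two columns multiply the rate by 0.95, the ceiling of the expected loss, and keep n at 400.

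| Basis for week-12 rate | Rate | Power | Rate after 5% loss | Power |
|---|---|---|---|---|
| Plan as written | 73% | 81.8% | 69.35% | 78.8% |
| Relative decline, constant pace | 70.2% | 79.4% | 66.7% | 77.0% |
| Decline in points, constant pace | 67% | 77.2% | 63.65% | 75.4% |

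**Descriptive limit and ratio at the 9-point margin.**

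- At 73%: 0.64 and 0.64/0.73 = 88%.
- At 67%: 0.58 and 0.58/0.67 = 87%.
- At 63.65%: 0.6365 − 0.09 = 0.5465, about 0.55, and 0.5465/0.6365 = 86%.

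**Scale.** At a 67% rate, 80% power would need 429 per arm by the same formula.

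**The case against.** The best defence is that nothing has been miscalculated. The subtraction is right, the 82% is right for 73%, and the plan openly states the drop it assumes for weeks 6 to 12. A similar trend need not mean an identical weekly rate, and a decline in switching could well slow. This stands in part: the fault lies in an input and its justification, not in the power computation. It does not remove the point, because the plan offers the observed trend as its basis and gives neither argument nor data for a slower pace.

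A second objection is that 77% is only one scenario. That also stands. The week-2 rate is not given, and the text does not say whether the 12% is absolute or relative, or whether it was seen in the menthol arm or overall. On the relative reading the shortfall is about 2.5 points and power is almost 80%.

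Third, the loss adjustment depends on two things the documents do not settle: whether loss reaches its ceiling, and whether the earlier trial's 85% already counted lost participants as non-switchers. At 2% loss the plan's 73% becomes 0.73 × 0.98 = 71.5%, with power of about 80.5%.

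A reader might infer that the true power is 75%, or that the trial is too small and its conclusion unsafe. The documents do not support either. The 75% combines the linear reading, loss at the ceiling and an 85% free of losses. The Aim 1 decision rule uses only the confidence interval and −0.09, never 73%, 0.64 or 88%, so the type 1 error and the analysis are unaffected. Every ratio above stays over the 80% criterion that the plan cites.

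**Conclusion.** The point holds as a mismatch between the planning rate and its stated basis. A 4-week decline is applied over 6 weeks, and neither constant-pace reading gives 73%. With truly equal arms, power is about 77% (67%, decline in points) or 79% (70%, relative decline). The chance of failing to show non-inferiority is then about 23% or 21%, against the 18% implied by the plan.

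The loss-as-failure rule is a separate and conditional reduction. If the 85% excludes losses and loss reaches 5%, power falls to about 79% at 73%, 77% at 70% and 75% at 67%.

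The effect is modest, but both constant-pace readings fall below 80%. The mismatch itself is certain from the text. The exact replacement rate is not, because the earlier trial's data are not in the documents. A genuine slowing after week 6 could support 73%, but the plan would have to say so.

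**What to change.** In II.C, do one of the following:

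1. Correct the extrapolation to the 6-week interval and restate the planning rate and power: 67% and about 77%, or 70% and about 79% if the 12% was relative.
2. Keep 73%, but replace the appeal to a similar trend with a statement, and a reason, that the decline is assumed to slow after week 6.

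In either case:

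- say whether the 12% is in points or relative, which group it comes from, and whether the 85% counted lost participants as non-switchers;
- show power over rates of about 64% to 73% (roughly 75% to 82%), including the rule for lost participants;
- match the descriptive limit and ratio to the rate used: 0.58 and 87% at 67%, or about 0.55 and 86% at 63.65%.

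The cost is some wording and a recomputed power statement, which will probably look slightly less favourable. No change is needed to the −0.09 margin, the decision rule or the 400 per arm.

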
Other outcomes of interest include tobacco harm reduction and EC acceptability. These constructs may be measured by the following:

**TOBACCO HARM REDUCTION** (Aim 2). Tobacco harm reduction is a global topic of interest among those transitioning from cigarettes to EC and is largely driven by reduction in CPD. We expect comparable rates of switching between groups and, therefore, comparable rates of tobacco harm reduction, defined as change in each of the following constructs from baseline to week 12.

• Tobacco Quality of Life Impact Tool ( $TQOLIT^{TM}v1$ ) will be used to assess was used to assess the impact of smoking/vaping on health-related quality of life.

- *Carbon Monoxide.* Carbon monoxide will be measured in parts per million (PPM) using a coVita Bedfont Micro+ Smokerlyzer at each study visit.
- *Blood Pressure.* Systolic and diastolic blood pressure will be measures with an Welch-Allyn blood pressure cuff.
- *Respiratory symptoms* have emerged as a primary concern among EC users and, therefore, we will carefully monitor respiratory symptoms over time using the following standardized measures:

• Lung function will be assessed via spirometry. We will summarize all values returned from the spirometer (i.e., FVC, FEV1, FEV1/FVC%, PEF) but will focus our attention on *FEF 25-75%*, the pulmonary function test of small airway disease that is most sensitive to effects of cigarette smoking.

 American Thoracic Society Questionnaire (ATSQ) will be used to assess common respiratory symptoms (e.g., cough first thing in the morning, wheezing, shortness of breath, etc.). This measure was selected because it contains items relevant to acute respiratory effects experienced by some cigarette smokers when they initiate EC.

• Leicester Cough Questionnaire (LCQ) is a valid, repeatable measure of chronic cough which is responsive to change, especially the onset of cough in established cigarette smokers when they initiate EC.

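### The power statement gives the non-inferiority limit (0.64) as the assumed tobacco EC rate; 82% power needs equal rates of 0.73, which it does not state

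*Combined protocol and SAP*

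**What the plan says.** Section II.C (Sample size, statistical methods, and power calculation) takes 0.73 as the menthol EC rate, P2. For the tobacco EC arm it writes "P1=the proportion in the tobacco EC group that will be complete or predominant switchers at week 12=0.64". The null hypothesis is P1 − P2 ≤ −0.09 and the alternative is P1 − P2 > −0.09. The section then states: "Following these assumptions 400 per group gives us 82% power with a Type 1 error rate of 2.5" percent, using a normal-approximation non-inferiority test.

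The same section uses 0.64 in a different role in two places. Just before defining P1, it says the tobacco EC proportion "will be similar to the menthol EC as long as it is greater than 64" percent. Later, in justifying the margin, it says "at this threshold the proposed effectiveness ratio for our study is 88% (.64/.73", with the ratio in brackets. In both places 0.64 is the lowest acceptable rate, not the expected one.

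Under Aim 1 in Statistical evaluation of study aims, non-inferiority requires the 95% confidence interval for P1 − P2 to have a lower limit above −0.09 and an upper limit of at least 0. That rule refers back to II.C for the definitions of P1 and P2.

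**The concern.** The power of a non-inferiority test is calculated at an assumed true difference inside the alternative, most often zero. The listed rates give 0.64 − 0.73 = −0.09, which is the edge of the null. At that point the probability of success is the type I error rate by construction, so 82% cannot follow from the assumptions as listed.

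This paragraph is the only justification for 800 participants, in a trial whose rationale is that a fully powered comparison is needed. A reader who enters the listed inputs cannot reproduce the figure. A reader who accepts the figure cannot see that it depends on the two flavors having exactly the same true rate.

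**Working it through.** **Inputs, all from II.C and Aim 1.** n = 400 per group; margin 0.09; P2 = 0.73; P1 as listed 0.64; type I error 2.5%. The sidedness is not stated. One-sided is implied by the directional alternative and by the use of the lower limit of a 95% interval.

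**Formula** (normal approximation, unpooled variance):

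SE = √[P1(1−P1)/n + P2(1−P2)/n]

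Power = Φ[(P1 − P2 + 0.09)/SE − 1.96]

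**Step 1: reproduce the plan's 82%.** Set P1 = P2 = 0.73. SE = √(2 × 0.1971/400) = 0.03139. Then 0.09/0.03139 = 2.867, and Φ(2.867 − 1.96) = Φ(0.907) = **81.8%**. This matches the stated figure.

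**Step 2: the inputs as listed.** Set P1 = 0.64 and P2 = 0.73. SE = √[(0.2304 + 0.1971)/400] = 0.03269. The numerator is 0.64 − 0.73 + 0.09 = 0, so power = Φ(−1.96) = **2.5%**.

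**Step 3: sensitivity to the unstated P1**, with P2 = 0.73 and n = 400:

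| True P1 | True difference | SE | Power |
|---|---|---|---|
| 0.73 | 0 | 0.03139 | 81.8% |
| 0.72 | −0.01 | 0.03157 | 71.7% |
| 0.71 | −0.02 | 0.03174 | 59.7% |
| 0.64 | −0.09 | 0.03269 | 2.5% |

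Exact binomial enumeration of the Aim 1 interval rule (Wald interval, both conditions) gives 81.9%, 71.8%, 59.8% and 2.5%, so the approximation is not the issue.

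**Step 4: could another calculation on 0.64 and 0.73 give 82%?** Superiority tests at 400 per group give 78.3% (two-sided 5%, pooled), 78.6% (unpooled), 69.2% (two-sided 2.5%) and 86.4% (one-sided 5%). None is within 2 points of 82%. With P2 held at 0.73, only P1 between about 0.728 and 0.732 is.

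**Step 5: does sample size matter at the listed inputs?** For the lower-limit test in II.C the numerator is zero at every n, so a larger trial does not raise the 2.5%. Under the two-part rule of Aim 1, the estimated difference must exceed −0.09 + 1.96·SE and also be at least −1.96·SE. At 400 per group these thresholds are −0.026 and −0.064, so the first governs and the result is 2.5%. The second governs once 2 × 1.96 × SE < 0.09, that is SE < 0.02296, or n above 0.4275/0.02296² ≈ 811 per group. Beyond that the chance falls below 2.5% (about 0.8% at 1,000 per group). Under the full rule 2.5% is therefore a ceiling.

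**The case against.** The strongest reply is that this is a slip of wording that the context mostly repairs. 0.64 is introduced as a limit, the null is written at −0.09, and the margin paragraph calls 0.64/0.73 a threshold. Elsewhere the plan looks forward to similar results: V.B, under Tobacco harm reduction (Aim 2), says "We expect comparable rates of switching between groups", and I.C says preliminary results "suggest comparable rates of switching from tobacco cigarettes to EC". An experienced reader would guess that the calculation was run at zero difference, and the 82% is then right.

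Much of that stands. It limits the point to labelling and omission. It does not remove it, because no section gives a tobacco EC rate, or a zero difference, as the power assumption. Other passages that seem to help do less than they appear to. The statement in I.A that "post-hoc analyses found equivalent rates of switching from tobacco cigarettes to EC" reports a past post-hoc result. The statement in II.B that "there is no data supporting this approach that menthol EC are more effective than tobacco EC" speaks only of missing evidence, and it continues by saying the same of the reverse. II.B also contemplates lower efficacy of tobacco EC as an acceptable trade.

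It is also fair to say that any non-inferiority trial powered at zero difference loses power this way, and that the documents give no estimate of a true deficit. The 1-point and 2-point figures show sensitivity only; they are not predictions.

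**Conclusion.** The point holds as an error in a stated power input. At P1 = 0.64 and P2 = 0.73 with 400 per group, the chance of declaring non-inferiority is 2.5%, not 82%. With P2 = 0.73 the stated 82% requires a true difference of 0, which the power statement omits. Power is about 72% at a true 1-point deficit and about 60% at 2 points. These figures rest on a one-sided 2.5% test, a margin of 0.09, and the plan's own 73% for menthol EC taken as given. Equal rates other than 0.73 give similar power (80.9% at 0.72, 82.7% at 0.74).

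Two stronger readings are tempting and are not supported:

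- A reader might infer that the trial is underpowered. It is not shown to be: under equal rates the arithmetic for 800 participants is sound.
- A reader might infer that success stays at 2.5% for any sample size under the plan's decision rule. That is true only of the lower-limit test in II.C. Under the two-part rule of Aim 1 the chance drops below 2.5% above about 811 per group. At the planned 400 the distinction makes no difference.

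That the software run used P1 = P2 = 0.73 is an inference from the match at 81.8%, since the output is not in the documents.

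**What to change.** Leave the sample size, the 9-point margin and the decision rule unchanged. In II.C:

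1. Keep P1 and P2 defined as the week-12 proportions of complete or predominant switchers in the tobacco EC and menthol EC groups. Aim 1 relies on these definitions, so the sentence should be edited, not deleted.
2. Remove 0.64 as the assumed value of P1.
3. After checking the PASS run, state: *Power is 82% at a true difference of 0 (P1 = P2 = 0.73); 0.64 is the tobacco EC rate at the non-inferiority limit P1 − P2 = −0.09 when P2 = 0.73, not the assumed rate.* If the run used other inputs, report those instead.
4. Optionally, add that power is about 72% if tobacco EC is truly 1 point worse and about 60% if 2 points worse.

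The cost is one or two sentences. The only downside is that the stated power is then visibly conditional on equal rates.
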